15.3 Recording/Documentation of AEs

Study staff will document in source documents and the appropriate AE Log CRF all AEs reported by or observed in enrolled study participants regardless of severity and presumed relationship to study procedures. AE severity will be graded per the DAIDS Table for Grading Adverse Events.

If an adverse event is identified the adverse events form will be completed. If a serious adverse event is identified, the serious adverse events form will be completed. Serious Adverse Events (SAEs) will be recorded and reported to the Provincial Director of Health and the DAIDS Medical Officer. All SAEs are being reported to review boards and sponsors per protocol.

15.4 Analysis/Management of AEs

Data will be obtained during the study visit, SMS text questionnaires, and through a study mobile number given to all participants to call for free if they feel that there are any complications due to an intervention they received.

Study participants will be given specific instructions (a phone call card) for contacting the study staff to report any untoward medical occurrences they feel they may experience. In the case of life-threatening events, participants will be instructed to seek immediate emergency care.

Emergency follow-up visit

Participants who reach out, request, or come in for an emergency follow-up visit will be seen as soon as possible.

For all emergencies, the field coordinator/study staff will:

- Ask the participant about the sequence of events since the intervention. Ask about: any problems; how problems developed; and any medication or other treatments obtained.
- Plan treatment of any problems that can be handled on an outpatient basis.
- Refer the participant to a higher level of care for treatment of potentially serious complications.
- Ensure that the means of communicating with and timely transport to a higher level health facility are available
- Note in the participant's research record all problems and actions taken.

15.5 Reporting Procedures of AEs and SAEs

- All adverse events (AEs): will be recorded in the adverse events form and will be reported to:
 - The field study coordinator, who will then communicate the adverse events to the Principal investigators.
 - Relevant Ministry of Health authorities
- Serious adverse events (SAEs): will be recorded on the serious adverse events form and reported to:
 - The field study coordinator, who will then communicate the adverse events to the Principal investigators.
 - The Provincial Director
 - DAIDS Medical Officer and Project Officer (sponsor).
 - Kenyan IRB and Yale IRB.

15.5.1 Specific Serious Adverse Event Requirements

All serious adverse events will be:

- recorded on the appropriate serious adverse event case report form
- followed through resolution by a study physician
- reviewed by a study physician (Kenyan PI)

Expedited Adverse Event Reporting Requirements

N/A. Our study does not involve a pharmacological agent, therefore does not fulfill the requirements, definitions, and methods for expedited adverse event reporting as outlined in Version 2.0 of the DAIDS Expedited Adverse Event (EAE) Manual, which is available on the DAIDS Regulatory Support Center (RSC) website at <http://rsc.tech-res.com/safetyandpharmacovigilance>.

15.6 Type and Duration of the Follow-up of Participants after Adverse Events

Participants who report any adverse event will be followed up weekly via SMS text or phone call until the adverse event is resolved.

15.7 Halting Rules for the Protocol

N/A. No pharmacologic or surgical interventions.

15.8 Premature Withdrawal of a Participant

See section 12.1.1.

15.9 Social Harms Monitoring and Reporting

It is possible that participants' involvement in the study could lead to social harms such as stigmatization, discrimination, disruption to social support network, abuse (physical/verbal). Social harms will be monitored closely throughout the study. Information on social harms will be solicited from participants during follow-up visits to examine their experiences. This information will be recorded on case report forms. If a participant reports social harms, study staff will make every effort to provide appropriate counseling, care, and referrals if necessary. Any social harms that are deemed to be serious or unexpected will be reported to the IRBs and reported to DAIDs.

Table 1: Evaluation Plan

Aims 1 and 2: Outcomes evaluated based on HIV prevention and treatment continua	Measures (Sources)	Data Collection Timeline	Data Analysis	N
Recruitment/Seek: Ability to recruit female youths that are high risk for HIV infection using two seek strategies (home-based vs. community-based). The proportion of youth in the community who accept study screening; the proportion of youth who accept enrollment.	CAPI baseline; (youth participants, total approached)	Baseline	Frequencies; differences in proportion by age, and recruitment strategy; which recruitment strategy yielded the highest rates of newly diagnosed HIV infection. Rates of acceptance of screening among potential participants offered screening and rates of enrollment among eligible participants will be compared by recruitment strategy using logistic regression. Risk will be characterized by number and serostatus of sex partners, concurrency, condom use, and patterns of HIV testing by the participant and any sex partners.	N=1200
Testing: Testing uptake; completion of confirmatory testing; proportion who are positive; among those who are positive, completion of baseline collection of CD4 and viral load tests.	GIRLS study project database	Baseline, 2 week SMS Satisfaction Survey.	Frequencies; multiple logistic regression for which testing approach most preferred/used by females. Age, risk behaviors, HIV testing history as predictors of preferences; which testing approach yielded the highest rates of newly diagnosed HIV infection.	N=1200
Linkage to Care: Percent of females who tested positive that attended a first HIV care appointment at a CCC; time to link to care after positive confirmatory result.	GIRLS study project database, medical record review at CCC, exit interviews.	2 weeks after first randomization; 1 week to re-randomize; 2 weeks after second randomization (5 weeks total from start of linkage pilot). Exit interview collected at 12 months.	Descriptive statistics; survival plots for occurrence and timing of linkage. Cox proportional hazards model for differences in likelihood and timing of linkage between the two treatment conditions; median time to linkage. Predictors of successful linkage to care.	N≈108
Retention in Care: Completion of viral load testing one year after positive confirmatory test; self-report of appointment attendance. Review of medical records to confirm self-report of clinic attendance.	SMS surveys, medical record review, exit interviews.	3, 6, 9, 12 months for SMS surveys. Medical record review to confirm clinic attendance self-report. Exit interview collected at 12 months.	Frequencies; assess number retained in care at 12 months. Proportion who complete viral load testing at 12 months.	N≈108
Primary Prevention: HIV risk behaviors, condom use, and HIV re-testing of a sub-sample of high risk HIV negatives	SMS surveys GIRLS study project database	6 and 12 months for SMS surveys. At 12 months, exit interview and re-testing	Descriptive statistics; new HIV diagnosis at 12 months.	N≈185
Aim 3 economic evaluation	Measures (Sources)	Data Collection Timeline	Data Analysis	
Economic evaluation to determine the comparative cost effectiveness of the seek, test, link, and prevention interventions.	GIRLS study project database	Accrual and follow-up period.	Micro-costing of the cost per HIV infected person under each seek and test strategy; incremental cost effectiveness of linkage to care intervention for HIV +; cost analysis of SMS intervention and re-testing for HIV negative females.	

15.10 Appropriate Methods and Timing for Analyzing Outcome Measures.

See Table 1: Evaluation Plan.

15.11 Sample Size Considerations

Baseline sample size calculation

Based on our experience with MP3 Youth (data not yet published), which screened N=788 female youth and enrolled N=690 female youth over a period of eight months (November 19, 2014 – June 12, 2015), we expect we can recruit N=1200 female youth over a period of around twice that time. We expect the sample accrual rate to be slower than in MP3 Youth, because we will be recruiting only female youth and mainly those out of school (a large proportion of younger MP3 Youth girls were in school and easier to recruit). In addition, we have two different recruitment strategies, and the home-based strategy may be more labor intensive and time consuming than a community mobile event. We therefore expect a somewhat lower accrual rate. Therefore, in order to stay within the estimate 12 months of recruitment, we will increase our field staff during the implementation phase of the project. Sample size estimates are also based on IRDO's program data and the estimated number of youth in Homa Bay. We expect large numbers of youth will be successfully recruited from the home and mobile events (IRDO reaches tens of thousands of youth/year) for a total sample size of ≥ 1200 female youth.

Power Analysis

Power calculations for Aim 1 are based on the yield of newly diagnosed HIV across recruitment strategies and testing options offered to female youth. Using version 12 of the PASS program (Hintze, 2013) for logistic regression, we did not approach this power analysis from the perspective of calculating a sample size needed to detect a particular effect size with at least 80% power. Rather, because this part of the study (Aim 1) is not a clinical trial but rather an exploration of preferences and yield of recruitment and participant-selected testing strategies, we started with the large, feasible sample size and determined the size of effects that could be detected with at least 80% power when comparing recruitment strategies and HIV testing approaches.

The expected percentage of girls testing positive is based on our MP3 Youth pilot study. In that study, 55 of 636 female youth not previously diagnosed were found to have HIV infection (data not yet published). Thus, we expect about 9% of all tested females in this study to have HIV infection not previously diagnosed.

With this estimate of the expected percentage of girls with newly diagnosed HIV infection, we asked how small of an increase in the odds of newly diagnosed HIV infection could be detected with 80% power when community-based recruitment is compared to home-based recruitment. With 600 youth recruited by each strategy, power is 80% to detect an odds ratio of 1.67, in other words, a modest increase from 9% to 14% newly diagnosed with HIV infection. When comparing testing approaches, and assuming an equal proportion of girls prefers each approach and testing approach does not interact with recruitment strategy, power is 80% to detect an odds ratio of 1.85. If there is an interaction between recruitment strategy and testing approach, when comparing

testing approaches within a recruitment strategy (i.e., estimating simple main effects), power is 80% to detect an odds ratio of 2.32.

These calculations show the proposed sample size (N=1200) is capable of detecting modest differences in the yield of newly diagnosed HIV infection across both recruitment strategies and testing approaches.

Among the approximately 108 female youth we expect to be newly diagnosed with HIV infection, about 20% are expected to successfully initiate HIV care at a health facility after a single SMS message. The remaining 80% (N=86) who are not linked to care after the initial SMS message will be randomly assigned to either continued SMS messages or to economic incentives. Assuming at least 60% are linked to care at some point during follow-up, survival analysis employing Cox regression will be able to detect a hazard ratio of 2.2 describing the impact of treatment condition (continued SMS vs. economic incentives) on the occurrence and timing of successful linkage to care at a health facility, with 80% power.

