There are numerous examples of individual HIV prevention interventions aimed at addressing the drivers of the HIV epidemic among youth. In the MP3 Youth study (data not yet published), we successfully reached 1740, recruited 1093 youth between the ages of 15-24 years old, carried out HIV testing for 1074, linked 69.7% of newly diagnosed HIV positives to care, and enrolled 284 for follow-up (HIV positive cohort: 106; PrEP cohort: 28; CCT cohort: 50, and HIV negatives: 100). From MP3 Youth, we learnt that we can reach and recruit youth in a mobile health care setting. In the GIRLS study, we will learn whether we can reach and recruit female youth in a home-based setting as well. In MP3 Youth we demonstrated that we were able to successfully test youth in a mobile health event setting, but unlike in the GIRLS study, MP3 Youth did not offer alternative options to staff provided rapid HIV testing, such as self-testing or referral to a health facility. In addition, although we successfully linked HIV infected participants in the MP3 Youth study to care and treatment using a one-time economic incentive (i.e., bus fare), the MP3 Youth study did not have SMS reminders as a linkage strategy. We were able to successfully verify school enrollment for the CCT cohort and will use similar procedures in the GIRLS study for linkage verification.

The Government of Kenya recently approved pre-exposure prophylaxis (PrEP) use as a national strategy for HIV prevention among key populations including high-risk females (Mukoma, 2016, NASCOP, 2015). PrEP is an HIV prevention method by which an uninfected individual takes antiretroviral drugs prior to HIV exposure to reduce the risk of infection (Plosker, 2013). Homa Bay is one of the selected counties that will offer PrEP, therefore, referrals will be made to government, private and NGO facilities offering the approved HIV prevention services, which includes PrEP.

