10.2 Target sample size

We project to reach 1,200 female youth over an accrual period of up to 12 months, plus one year of follow-up. Therefore, in order to stay within the estimate 12 months of recruitment, we will put in place adequate field staff during the implementation phase of the project.

Because Aim 1 of this study is not a clinical trial, but rather an exploration of differences in the yield of previously undiagnosed HIV infection across recruitment and testing strategies, we started with this large and feasible sample size and conducted power calculations to determine the size of effects detectable with at least 80% power. By recruiting 1200 female youth between the age of 15-24 years, we will have 80% power to detect an odds ratio of 1.67 when comparing recruitment strategies, on the proportion of previously undiagnosed female youth testing positive for HIV infection. And when comparing testing approaches within a recruitment strategy on that same outcome, an odds ratio of 2.01 can be detected with 80% power. These calculations, which are presented in more detail in section 15.11, show the proposed sample size (N=1200) is capable of detecting modest differences in the yield of previously undiagnosed HIV infection across both recruitment strategies and testing approaches.

We expect large numbers of youth to participate through both venues (IRDO reaches tens of 1000s of youth/year). Based on our experience with MP3 Youth (data not yet published) study (KNH/UON ERC P23/03/2011), which screened N=788 female youth and enrolled N= 690 female youth over a period of 8 months (November 19, 2014 – June 12, 2015) in the same county, we anticipate that we will be able to recruit 1,200 females over a period of 12 months with enhanced recruitment effort. We expect the sample accrual rate to be slower than in MP3 Youth, because we will be recruiting only female youth and mainly those out of school (a large proportion of younger MP3 Youth girls were in school and easier to recruit). In addition, we have two different recruitment strategies, and the home-based strategy may be more labor intensive and time consuming than a community mobile event. We therefore expect a somewhat lower accrual rate.

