The sample size for the linkage to care adaptive intervention pilot is an estimate of the number of female youth with previously undiagnosed HIV infection we anticipate reaching. The expected percentage of girls testing positive was based on our MP3 Youth pilot study (data not yet published), and we expect 9% of all tested girls to have HIV infection not previously diagnosed. Thus given a total sample size of 1,200 female youth, we anticipate enrolling about 108 previously undiagnosed HIV positive females in the adaptive intervention pilot to link HIV positive female youth to HIV treatment and care.

Sampling method: We will stratify the sample by conveniently selected sub-counties; Homa Bay municipality, Mbita sub-county and Ndhiwa sub-county. Mapping of catchment areas surrounding health facilities will be used to establish relationships with referral clinics. We select a random starting point that is within walking distance (about 5km) of the catchment area of the health facility. Approximately four hundred (400) participants will be recruited from each stratum and for each stratum it is assumed that 200 participants will be recruited through each recruitment approach. Both recruitment strategies (household and mobile event) will run concurrently until the desired sample size is reached. If needed for sample size attainment, we will expand the sampling area to a 6 - 10 km circumference of the referral clinic.

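### The 80% power at odds ratio 1.67 for the venue comparison puts 9% in the lower-yield venue, but the plan expects 9% overall; on that basis power is about 71% and the detectable odds ratio about 1.78

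*Combined protocol and SAP*

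**What the plan says.** Section 15.11 derives the expected yield from the pilot study, where 55 of 636 girls without an earlier diagnosis tested positive, and concludes that "we expect about 9% of all tested females in this study to have HIV infection not previously diagnosed". Section 10.2 applies the same 9% to the full 1,200: "we anticipate enrolling about 108 previously undiagnosed HIV positive females in the adaptive intervention pilot". The protocol summary, section 11.4 and the randomisation section also plan on about 108.

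Section 15.11 then bases the venue power calculation on this estimate: "power is 80% to detect an odds ratio of 1.67, in other words, a modest increase from 9% to 14" per cent, with 600 girls per venue. It adds detectable odds ratios of 1.85 for testing approaches pooled over venues and 2.32 within a venue. Section 10.2 repeats the venue figure without the pair of rates: "we will have 80% power to detect an odds ratio of 1.67 when comparing recruitment strategies".

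On the pilot's setting, section 7.2.1 says "we learnt that we can reach and recruit youth in a mobile health care setting" and presents home-based recruitment as something this study will learn about. In section 13.2 the reference category for the yield model is facility testing after community recruitment, and the home effect is left free to go either way. Alpha and sidedness are not given.

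**The concern.** The plan uses the same 9% for two different quantities. For the size of the positive cohort it is the yield over both venues together. In the power statement it is the yield in the lower of the two venues. Both hold only if the venues do not differ, and the power statement supposes that they do.

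Newly diagnosed infection is the endpoint that section 13.2 names for comparing venues and testing approaches. The detectable odds ratios are the only statistical support offered for 1,200, and both sections conclude that modest differences can be found. If the figures are more favourable than the plan's own expected yield allows, a null venue comparison may be read as stronger evidence of similar yield than it is.

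**Working it through.** **Inputs.** 600 per venue, odds ratio 1.67, rates of 9% and about 14%, and 80% power (15.11). Overall yield 9%, or 108 of 1,200 (10.2 and 15.11). Assumption: two-sided alpha 0.05, since none is stated.

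**Formulas.** The rate at odds ratio OR above p1 is p2 = p1·OR / (1 − p1 + p1·OR). With p̄ the mean of the two rates and n the number per group,

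power = Φ{ [ |p2 − p1|·√n − 1.96·√(2p̄(1 − p̄)) ] / √(p1(1 − p1) + p2(1 − p2)) }.

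The logistic-regression formula for a binary covariate gives identical results.

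**1. The plan's own figure.** With p1 = 0.09, p2 = 0.1503/1.0603 = 0.1418. Then (0.05175 × 24.495 − 1.96 × 0.45266)/0.45117 = 0.843, so power is 80.0%. The stated figure reproduces, and simulation gives 80.1–80.3%. One-sided 0.05 would give 87.7%, so two-sided 0.05 appears to be what was used. Expected positives: 600 × 0.09 + 600 × 0.1418 = 139, or 11.6% of 1,200.

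**2. 9% as the overall yield.** Solving (p1 + p2)/2 = 0.09 with OR 1.67 gives 6.93% and 11.07%, hence 108 positives. Then (0.04132 × 24.495 − 1.96 × 0.40472)/0.40367 = 0.542, so power is 70.6% (simulation 70.5–70.7%). The odds ratio with 80% power is 1.78 (6.7% against 11.3%).

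**3. 9% as the community yield.**
- Home higher: 9.0% against 14.2%, the pair in step 1, with 80.0% power.
- Home lower: 5.59% against 9.0%. Then (0.03409 × 24.495 − 1.96 × 0.36779)/0.36699 = 0.311, so power is 62.2% (simulation 62.4–62.5%). The odds ratio with 80% power is 1.92. Expected positives: 600 × (0.0559 + 0.09) = 88.

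Neither of these two cases returns 108 positives; only step 2 does.

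**4. Testing approaches.** The companion figures reproduce with 9% as the lower rate: OR 1.85 with 400 per group (9.0% against 15.5%) has 79.8% power, and OR 2.32 with 200 per group (9.0% against 18.7%) has 80.2%. With three approaches, an overall 9% does not fix the mean of any one pair, so the result depends on the third arm. The table assumes equal uptake, a mean of 9% over the three arms and, for the last column, a 9% yield in that venue.

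| Third arm | Detectable OR, pooled (400 per arm) | Detectable OR, within a venue (200 per arm) |
|---|---|---|
| Shares the lower rate | 1.97 (7.0% vs 13.0%) | 2.63 (6.2% vs 14.7%) |
| Is at 9% | 2.04 | 2.84 |
| Shares the higher rate | 2.12 (5.4% vs 10.8%) | 3.10 (4.0% vs 11.5%) |

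**The case against.** The strongest reply is that nothing is miscalculated. Section 15.11 prints its pair of rates beside the power, asks only about an increase in the odds, and is right for that pair. This stands: a reader might infer an arithmetic error, and there is none. What remains is that the printed pair does not fit the yield expected in the same section, and that section 10.2 repeats the 80% without the pair.

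A second reply concerns the source of the 9%. Since it comes from a mobile-setting pilot, a reader might infer that true power is 62%. The documents do not support that. Section 15.11 does speak of an increase when community is compared with home, but section 13.2 makes community the reference and lets home move the odds up or down. With community at 9% and home higher, the printed calculation is exactly right. The 62% applies only if home yields less.

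Third, Aim 1 is described as exploratory, the sample size was set by feasibility with power computed afterwards, and 108 is labelled an estimate. This also stands and limits the severity. A reader might infer that 1,200 is too few and must rise; no such conclusion follows.

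Finally, one-sided 0.05 at an overall 9% would give 80.5%. Its rates, 6.9% and 11.1%, contradict the printed 9% to 14%, so it does not explain the figure.

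**Conclusion.** The point holds as an inconsistency of inputs. The 80% at odds ratio 1.67 is right only when 9% is the yield in the lower-yield venue. On the plan's own overall 9%, power is about 71% and the detectable odds ratio about 1.78. This result needs no assumption about which venue does better; it rests on 600 tested per venue and two-sided alpha 0.05. The 62% and 1.92 are conditional on community at 9% and home lower.

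For testing approaches the direction is the same but the size is less certain: about 1.97–2.12 pooled and 2.63–3.10 within a venue if two of the three arms share a rate. Without that restriction the printed figure can coexist with an overall 9%; for example, arms at 9.0%, 15.5% and 2.5% average 9% and contain the 1.85 pair. Severity is minor to moderate.

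**What to change.** In sections 10.2 and 15.11:

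- Give the venue figure as an odds ratio of about 1.78 at an overall yield of 9% (108 positives). Say that 1.67 holds only when 9% is the lower-yield rate, and that 1.92 applies when it is the higher-yield rate.
- State alpha and sidedness.
- For testing approaches, say that 1.85 and 2.32 also take 9% as the lower rate. Give the overall-9% values as approximate and dependent on the third arm (about 1.97–2.12 pooled, 2.63–3.10 within a venue), with the equal-uptake and 9%-per-venue assumptions written out.
- While editing, reconcile the within-strategy odds ratio, which is 2.01 in 10.2 and 2.32 in 15.11.
- Reconsider whether modest is the right word for the within-venue differences.

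The cost is wording only. The sample size, conduct and analysis are unchanged; the stated detectable effects become somewhat larger, most visibly within a venue.
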